7.3. Variables

The described variables are classified into two variable groups according to the role, the clinical outcome and baseline (demographic, clinical, treatment variables). The latter include the possible subgroups to consider. These analyses are initially exploratory to the extent that the specific analyses may be performed according to the sample collected.

Table 1. Table of Variables

Variable	Role	Data source (s)	Operational definition
Age	Demographic characteristic	Medical record	Birthday
Gender	Demographic characteristic	Medical record	Male, female, other
Race	Demographic characteristic	Medical record	White, half-breed, indigenous, black, others
Weight	Demographic characteristic	Medical record	Kg
Height	Demographic characteristic	Medical record	Mt (meters)
Body mass index	Demographic characteristic	Medical record	Kg/mt ²
City of residence	Demographic characteristic	Medical record	Cities of Colombia
Time to diagnosis to NVAF	Clinical characteristic	Medical record	Date (dd/mm/yy)
High alcohol intake at OAC prescription date	Clinical characteristic	Medical record	Yes, No

Variable	Role	Data source (s)	Operational definition
Diabetes	Clinical characteristic	Medical record	No, without chronic complication, with end-organ damage
Liver disease	Clinical characteristic	Medical record	No, mild, moderate, severe
Hypertension	Clinical characteristic	Medical record	Diagnosis of hypertension (Yes, No)
Uncontrolled hypertension at OAC prescription date	Clinical characteristic	Medical record	Yes, No
Rheumatic disease	Clinical characteristic	Medical record	Yes, No
Acquired Immune Deficiency Syndrome (AIDS)	Clinical characteristic	Medical record	Yes, No
Severe renal disease (dialysis, organ transplant)	Clinical characteristic	Medical record	Yes, No
Moderate renal disease (creatinine > 3 mg/dL)	Clinical characteristic	Medical record	Yes, No
Chronic heart failure	Clinical characteristic	Medical record	Yes, No
Myocardial infarction	Clinical characteristic	Medical record	Yes, No
Chronic obstructive pulmonary disease (COPD)	Clinical characteristic	Medical record	Yes, No
Peripheral vascular disease	Clinical characteristic	Medical record	Yes, No
Stroke or transient ischemic attack (TIA)	Clinical characteristic	Medical record	Yes, No
Dementia	Clinical characteristic	Medical record	Yes, No
Hemiplegia	Clinical characteristic	Medical record	Yes, No
Connective tissue disease	Clinical characteristic	Medical record	Yes, No

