E121	Malnutrition-related diabetes mellitus with ketoacidosis
E126	Malnutrition-related diabetes mellitus with other specified complications
E128	Malnutrition-related diabetes mellitus with unspecified complications
E129	Malnutrition-related diabetes mellitus without complications

PFIZER CONFIDENTIAL

ICD-10	Description
E130	Other specified diabetes mellitus with coma
E131	Other specified diabetes mellitus with ketoacidosis
E136	Other specified diabetes mellitus with other specified complications
E138	Other specified diabetes mellitus with unspecified complications
E139	Other specified diabetes mellitus without complications
E140	Unspecified diabetes mellitus with coma
E141	Unspecified diabetes mellitus with ketoacidosis
E146	Unspecified diabetes mellitus with other specified complications
E148	Unspecified diabetes mellitus with unspecified complications
E149	Unspecified diabetes mellitus without complications

2 point each:

▪ *Hemiplegia or paraplegia*

ICD-10	Description
G81	Hemiplegia
G82	Paraplegia and tetraplegia
G041	Tropical spastic paraplegia
G114	Hereditary spastic paraplegia
G801	Spastic diplegia
G802	Infantile hemiplegia
G830	Diplegia of upper limbs
G831	Monoplegia of lower limb
G832	Monoplegia of upper limb
G833	Monoplegia, unspecified
G834	Cauda equina syndrome
G839	Paralytic syndrome, unspecified
G81	Hemiplegia
G82	Paraplegia and tetraplegia
G041	Tropical spastic paraplegia
G114	Hereditary spastic paraplegia
G801	Spastic diplegia
G802	Infantile hemiplegia
G830	Diplegia of upper limbs
G831	Monoplegia of lower limb
G832	Monoplegia of upper limb
G833	Monoplegia, unspecified
G834	Cauda equina syndrome
G839	Paralytic syndrome, unspecified

▪ *Moderate or severe renal disease*

ICD-10	Description
N18	Chronic renal failure
N19	Unspecified renal failure
N052	Diffuse membranous glomerulonephritis
N053	Diffuse mesangial proliferative glomerulonephritis
N054	Diffuse endocapillary proliferative glomerulonephritis
N055	Diffuse mesangiocapillary glomerulonephritis
N056	Dense deposit disease
N057	Diffuse crescentic glomerulonephritis

PFIZER CONFIDENTIAL

ICD-10	Description
N250	Renal osteodystrophy
I120	Hypertensive renal disease with renal failure
I131	Hypertensive heart and renal disease with renal failure
N032	Diffuse membranous glomerulonephritis
N033	Diffuse mesangial proliferative glomerulonephritis
N034	Diffuse endocapillary proliferative glomerulonephritis
N035	Diffuse mesangiocapillary glomerulonephritis
N036	Dense deposit disease

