N037	Diffuse crescentic glomerulonephritis
Z490	Preparatory care for dialysis
Z491	Extracorporeal dialysis
Z492	Other dialysis
Z940	Kidney transplant status
Z992	Dependence on renal dialysis

▪ *Diabetes with end-organ damage*

ICD-10	Description
E102	Insulin-dependent diabetes mellitus with renal complications
E103	Insulin-dependent diabetes mellitus with ophthalmic complications
E104	Insulin-dependent diabetes mellitus with neurological complications
E105	Insulin-dependent diabetes mellitus with peripheral circulatory complications
E107	Insulin-dependent diabetes mellitus with multiple complications
E112	Non-insulin-dependent diabetes mellitus with renal complications
E113	Non-insulin-dependent diabetes mellitus with ophthalmic complications
E114	Non-insulin-dependent diabetes mellitus with neurological complications
E115	Non-insulin-dependent diabetes mellitus with peripheral circulatory complications
E117	Non-insulin-dependent diabetes mellitus with multiple complications
E122	Malnutrition-related diabetes mellitus with renal complications
E123	Malnutrition-related diabetes mellitus with ophthalmic complications
E124	Malnutrition-related diabetes mellitus with neurological complications
E125	Malnutrition-related diabetes mellitus with peripheral circulatory complications
E127	Malnutrition-related diabetes mellitus with multiple complications
E132	Other specified diabetes mellitus with renal complications
E133	Other specified diabetes mellitus with ophthalmic complications
E134	Other specified diabetes mellitus with neurological complications
E135	Other specified diabetes mellitus with peripheral circulatory complications
E137	Other specified diabetes mellitus with multiple complications
E142	Unspecified diabetes mellitus with renal complications
E143	Unspecified diabetes mellitus with ophthalmic complications
E144	Unspecified diabetes mellitus with neurological complications
E145	Unspecified diabetes mellitus with peripheral circulatory complications
E147	Unspecified diabetes mellitus with multiple complications
E102	Insulin-dependent diabetes mellitus with renal complications
E103	Insulin-dependent diabetes mellitus with ophthalmic complications
E104	Insulin-dependent diabetes mellitus with neurological complications
E105	Insulin-dependent diabetes mellitus with peripheral circulatory complications
E107	Insulin-dependent diabetes mellitus with multiple complications
E112	Non-insulin-dependent diabetes mellitus with renal complications

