C84	Peripheral and cutaneous T-cell lymphomas
C85	Other and unspecified types of non-Hodgkin's lymphoma
C88	Malignant immunoproliferative diseases
C90	Multiple myeloma and malignant plasma cell neoplasms
C91	Lymphoid leukaemia
C92	Myeloid leukaemia
C93	Monocytic leukaemia
C94	Other leukaemias of specified cell type
C95	Leukaemia of unspecified cell type
C96	Other and unspecified malignant neoplasms of lymphoid, haematopoietic and related tissue
C97	Malignant neoplasms of independent (primary) multiple sites

3 points each:

- *Moderate or severe liver disease*

ICD-10	Description
K704	Alcoholic hepatic failure
K711	Toxic liver disease with hepatic necrosis
K721	Chronic hepatic failure
K729	Hepatic failure, unspecified
K765	Hepatic veno-occlusive disease
K766	Portal hypertension
K767	Hepatorenal syndrome
I850	Oesophageal varices with bleeding
I859	Oesophageal varices without bleeding
I864	Gastric varices
I982	Oesophageal varices in diseases classified elsewhere

6 points each:

- *Metastatic solid tumor*

ICD-10	Description
C77	Secondary and unspecified malignant neoplasm of lymph nodes
C78	Secondary malignant neoplasm of respiratory and digestive organs
C79	Secondary malignant neoplasm of other sites
C80	Malignant neoplasm without specification of site

- *Human immunodeficiency virus (HIV)-AIDS*

ICD-10	Description
B20	Human immunodeficiency virus [HIV] disease resulting in infectious and parasitic diseases
B21	Human immunodeficiency virus [HIV] disease resulting in malignant neoplasms
B22	Human immunodeficiency virus [HIV] disease resulting in other specified diseases
B24	Unspecified human immunodeficiency virus [HIV] disease
Z21	Asymptomatic human immunodeficiency virus [HIV] infection status

One point was added to the total score of the Charlson index for each decade after the age of 50 years:

50 to 59: 1 point,

60 to 69: 2 points,

70 to 79: 3 points,

80 to 89: 4 points,

>90: 5 points.

- **CHA₂DS₂-VACs score:** The CHA₂DS₂-VACs score will be used to analyze the effect of stratification of the risk of stroke. CHA₂DS₂-VACs scores range from 0 to 9. ICD-10 diagnostic codes for each component of the index when applicable:
 - **C:** I11.0, I13.0, I13.2, I50
Score 1 point

ICD-10	Description
I110	Hypertensive heart disease with (congestive) heart failure
I130	Hypertensive heart and renal disease with (congestive) heart failure
I132	Hypertensive heart and renal disease with both (congestive) heart failure and renal failure
I50	Heart failure

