H: I10, I11, I12, I13, I15

Score 1 point

ICD-10	Description
I10	Essential (primary) hypertension
I11	Hypertensive heart disease
I12	Hypertensive renal disease
I13	Hypertensive heart and renal disease
I15	Secondary hypertension

A: Age \geq 75 years

Score 2 points

D: E10 a E14

Score 1 point

ICD-10	Description
E10	Insulin-dependent diabetes mellitus
E11	Non-insulin-dependent diabetes mellitus
E12	Malnutrition-related diabetes mellitus
E13	Other specified diabetes mellitus
E14	Unspecified diabetes mellitus

S2: G45.0, G45.1, G45.2, G45.3, G45.8, G45.9

Score 2 points

ICD-10	Description
G450	Vertebral-basilar artery syndrome
G451	Carotid artery syndrome (hemispheric)
G452	Multiple and bilateral precerebral artery syndromes
G453	Amaurosis fugax
G458	Other transient cerebral ischaemic attacks and related syndromes

V: I26, I82, I21- I25, I65, I70- I72, I73.1, I73.8, I73.9, I79.0, I79.2, K55.1, K55.8, K55.9, Z95.8, Z95.9

Score 1 point

ICD-10	Description
I26	Pulmonary embolism
I82	Other venous embolism and thrombosis
I21	Acute myocardial infarction
I22	Subsequent myocardial infarction
I23	Certain current complications following acute myocardial infarction
I24	Other acute ischaemic heart diseases
I25	Chronic ischaemic heart disease
I65	Occlusion and stenosis of precerebral arteries, not resulting in cerebral infarction
I70	Atherosclerosis
I71	Aortic aneurysm and dissection
I72	Other aneurysm
I731	Thromboangiitis obliterans [Buerger]
I738	Other specified peripheral vascular diseases
I739	Peripheral vascular disease, unspecified
I790	Aneurysm of aorta in diseases classified elsewhere
I792	Peripheral angiopathy in diseases classified elsewhere
K551	Chronic vascular disorders of intestine
K558	Other vascular disorders of intestine

A: Age 64-74 years

Score 1 point

Sc: Sex category (female)

Score 1

- **HASBLED score:** The HAS-BLED score will be used to analyze the risk of bleeding. The modified HAS-BLED score ranges from 0 to 8. ICD-10 diagnostic codes for each component of the index when applicable:

•

H: I10, I11, I12, I13, I15

Score 1 point

ICD-10	Description
I10	Essential (primary) hypertension
I11	Hypertensive heart disease
I12	Hypertensive renal disease
I13	Hypertensive heart and renal disease
I15	Secondary hypertension

Apixaban

B0661148- NON-INTERVENTIONAL STUDY PROTOCOL

Final, 10 October 2019

A: N03.2, N03.3, N03.4, N03.5, N03.6, N03.7, N05.2, N05.3, N05.4, N05.5, N05.6, N057, N18- N19, N25.0, Z49.0, Z49.2, Z94.0, Z99.2

Score 1 point

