ICD-10	Description
N032	Diffuse membranous glomerulonephritis
N033	Diffuse mesangial proliferative glomerulonephritis
N034	Diffuse endocapillary proliferative glomerulonephritis
N035	Diffuse mesangiocapillary glomerulonephritis
N036	Dense deposit disease
N037	Diffuse crescentic glomerulonephritis
N052	Diffuse membranous glomerulonephritis
N053	Diffuse mesangial proliferative glomerulonephritis
N054	Diffuse endocapillary proliferative glomerulonephritis
N055	Diffuse mesangiocapillary glomerulonephritis
N056	Dense deposit disease
N057	Diffuse crescentic glomerulonephritis
N18	Chronic renal failure
N19	Unspecified renal failure
N250	Renal osteodystrophy
Z490	Preparatory care for dialysis
Z492	Other dialysis
Z940	Kidney transplant status
Z992	Dependence on renal dialysis

A: B18, I85, I86.4, I98.2, K70, K71.1, K71.3, K71.4, K71.5, K71.7, K72.1, K72.9, K73, K74, K76.0, K76.2, K76.3, K76.4, K76.5, K76.6, K76.7, K76.8, K76.9, Z94.4

Score 1 point

ICD-10	Description
B18	Chronic viral hepatitis
I85	Oesophageal varices
I864	Gastric varices
I982	Oesophageal varices in diseases classified elsewhere
K70	Alcoholic liver disease
K711	Toxic liver disease with hepatic necrosis
K713	Toxic liver disease with chronic persistent hepatitis
K714	Toxic liver disease with chronic lobular hepatitis
K715	Toxic liver disease with chronic active hepatitis
K717	Toxic liver disease with fibrosis and cirrhosis of liver
K721	Chronic hepatic failure
K729	Hepatic failure, unspecified
K73	Chronic hepatitis, not elsewhere classified
K74	Fibrosis and cirrhosis of liver
K760	Fatty (change of) liver, not elsewhere classified
K762	Central haemorrhagic necrosis of liver
K763	Infarction of liver
K764	Peliosis hepatis
K765	Hepatic veno-occlusive disease
K766	Portal hypertension
Z944	Liver transplant status

S: I64, I69.3, D62, D68.3, D69.8, D69.9, H31.3, H35.6, H43.1, H45.0, H92.2, I23.0, I31.2

Score 1 point

PFIZER CONFIDENTIAL

ICD-10	Description
I64	Stroke, not specified as haemorrhage or infarction
I693	Sequelae of cerebral infarction
D62	Acute posthaemorrhagic anaemia
D683	Haemorrhagic disorder due to circulating anticoagulants
D698	Other specified haemorrhagic conditions
D699	Haemorrhagic condition, unspecified
H313	Choroidal haemorrhage and rupture
H356	Retinal haemorrhage
H431	Vitreous haemorrhage
H450	Vitreous haemorrhage in diseases classified elsewhere
H922	Otorrhagia
I230	Haemopericardium as current complication following acute myocardial infarction

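### The HAS-BLED renal item omits Z49.1, I12.0 and I13.1, which the protocol's own Charlson renal list includes, so patients with no other listed renal code score one point too low

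*Combined protocol and SAP*

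**What the plan says.** Section 7.3.1 defines each HAS-BLED component by ICD-10 codes where these apply. The renal part of item A, worth one point, begins "A: N03.2, N03.3, N03.4, N03.5, N03.6, N03.7, N05.2, N05.3, N05.4, N05.5, N05.6, N057" and ends "N18- N19, N25.0, Z49.0, Z49.2, Z94.0, Z99.2". The table under that line repeats the same codes: the row for Z49.0 ("Preparatory care for dialysis") is followed directly by Z49.2. In HAS-BLED, I12 and I13 appear only under item H (hypertension).

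The same section builds a Charlson index whose moderate-or-severe renal category scores two points. That list includes Z49.1 ("Extracorporeal dialysis"), I12.0 ("Hypertensive renal disease with renal failure") and I13.1 ("Hypertensive heart and renal disease with renal failure").

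I13.2 is described as "Hypertensive heart and renal disease with both (congestive) heart failure and renal failure". It is listed under Charlson heart failure and under item C of CHA2DS2-VASc, but in neither renal list.

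Table 1 (Section 7.3) gives the medical record as the source of the HAS-BLED score. It also collects two yes/no renal fields from the chart: a moderate one, defined by creatinine above 3 mg/dL, and a severe one, "Severe renal disease (dialysis, organ transplant".

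**The concern.** The two renal lists are almost identical, and the protocol gives no reason for the codes on which they differ. Keeping preparatory care for dialysis and other dialysis while leaving out extracorporeal dialysis looks like a transcription slip. The two hypertensive codes are renal failure by their own labels.

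Followed as written, the plan can describe the same patient as having moderate or severe renal disease in one baseline score and no renal abnormality in another. Any error runs in one direction, towards a lower bleeding-risk score. Baseline characteristics are a primary objective (Section 6), and Section 7.3.1 assigns HAS-BLED to the analysis of bleeding risk, so an error would also carry into any subgroup formed on that score. Renal failure and dialysis are not exclusions in Section 7.2.2, so such patients can enter the cohort.

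**Working it through.** The plan states no figure to reproduce. The check is a comparison of two code lists, followed by scoring patients who carry a single code.

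**Inputs (all Section 7.3.1)**
- Charlson renal list: N18, N19 (2); N03.2 to N03.7 (6); N05.2 to N05.7 (6); N25.0 (1); I12.0, I13.1 (2); Z49.0, Z49.1, Z49.2, Z94.0, Z99.2 (5). Total 2 + 6 + 6 + 1 + 2 + 5 = 22.
- HAS-BLED item A, renal: N18, N19 (2); N03.2 to N03.7 (6); N05.2 to N05.7 (6); N25.0 (1); Z49.0, Z49.2, Z94.0, Z99.2 (4). Total 2 + 6 + 6 + 1 + 4 = 19. The code line and the table contain the same 19.

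**Set difference**
- Charlson minus HAS-BLED = {I12.0, I13.1, Z49.1}; 22 − 19 = 3.
- HAS-BLED minus Charlson = empty.

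**Scores for a patient with one renal code only**

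| Code | HAS-BLED renal | HAS-BLED H | Charlson renal | Charlson heart failure |
|---|---|---|---|---|
| Z49.1 | 0 | 0 | 2 | 0 |
| I12.0 | 0 | 1 | 2 | 0 |
| I13.1 | 0 | 1 | 2 | 0 |
| I13.2 | 0 | 1 | 0 | 1 |

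The first three rows are the inconsistency between the scores. The fourth is a separate gap: I13.2 earns its hypertension and heart-failure points but no renal point in either score, so aligning HAS-BLED with the present Charlson list would not close it.

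**Could the omission be deliberate?** Two comparisons within Section 7.3.1 suggest not.
- The HAS-BLED liver code line covers every code in the two Charlson liver lists, so reuse of the Charlson codes was complete for liver and incomplete for renal.
- Avoiding double credit with hypertension does not explain it. In CHA2DS2-VASc, I11.0, I13.0 and I13.2 score under C and, through I11 and I13, under H as well. That reason could not apply to Z49.1 in any case.

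**Size.** The loss is one point per affected patient. If a proportion p of the 7,500 patients have one or more of the three codes and no other listed renal code, then 7,500 × p patients are under-scored and the cohort mean HAS-BLED is too low by p points. The documents give nothing from which to estimate p.

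**The case against.** The case for leaving this alone has four parts.

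1. *Most renal patients are still caught.* N18, N19, Z49.0, Z49.2, Z94.0 and Z99.2 all remain in item A. This stands. A reader might infer that HAS-BLED is too low in dialysis patients, or in severe renal disease generally. The documents do not support that: the point is lost only when no other listed code is present, and how often that happens is unknown. For the same reason they support no head count.

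2. *The chart may supply the item.* Table 1 sources HAS-BLED from the medical record and collects renal disease there, trained physicians abstract the data (Section 7.6.1), and the ICD-10 codes apply only where applicable. This stands in part, because codes may not be the only route to the point. But no rule links the chart fields to item A. Table 2 offers no fallback either, since its row labelled renal disease lists liver codes.

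3. *Different scores need not share a list.* True in principle, and weightier for I12.0 and I13.1, whose patients already receive the hypertension point. But that point is for a different item, the labels of both codes state renal failure, and the argument does not explain the missing dialysis code.

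4. *Little depends on it.* The study is descriptive and Section 7.7 rules out treatment comparison. No outcome definition or eligibility rule uses HAS-BLED. This stands and limits the importance of the point.

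**Conclusion.** The point holds as a minor code-list error. Applied as printed, item A gives 0 renal points to a patient whose only renal coding is Z49.1, I12.0 or I13.1, while Charlson gives that patient 2. HAS-BLED is then one point too low. I13.2 is a related but separate omission from both renal lists.

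This assumes that item A is scored from the printed codes, as Section 7.3.1 indicates, and that some patients carry one of these codes without another listed one. The list difference itself is certain; the number of patients it touches cannot be derived from the documents and may be very small. Nor should a reader infer bias in a comparison between anticoagulants, because none is planned. The effect is confined to the baseline description and to any subgroup based on HAS-BLED.

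**What to change.** - Add Z49.1, I12.0 and I13.1 to HAS-BLED item A, in both the code line and the table. This takes the list from 19 to 22 entries, matching the present Charlson renal list.
- Add I13.2 to both renal lists (22 + 1 = 23 entries each), leaving its heart-failure and hypertension credit unchanged.
- State whether the Table 1 renal fields also feed item A. They may supplement the codes, with the point given if either a listed code or a chart field is positive. They should not replace the codes: the chart fields require creatinine above 3 mg/dL, dialysis or transplant, so patients coded N18, N19 or N03/N05 who fall short of those criteria would lose the point.
- If any of the omissions is intended, give the reason in Section 7.3.1.

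The cost is an edit to the code lists before the scores are derived. No new variable has to be collected.

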7.3.1. Definition of outcome variables

- **OAC escalation:** The dose escalation of the OAC dose will be considered as a dose frequency according to the index dose, as well as the follow-up doses. The proportion of patients experiencing "dose increase", "dose decrease" or "no change" during follow-up with respect to the index dose will be measured, and the time to dose increase or decrease will be calculated.

C
C
I

C
C
I

- **Switch of treatment:** A switch among anticoagulants will be defined as a prescription filled for non-index anticoagulants within +/- 30 days after the date of discontinuation.
- **Persistence:** Persistence will be defined as the time under OAC therapy, calculated as the time in days from the index date to the date of discontinuation or change to treatment. As previously stated, discontinuation will be defined as a change of treatment, that is, to another OAC, or when there is no evidence of a prescription for 60 days from the last supply delivered, whichever comes first.

Therefore, if a patient does not receive his next prescription for the OAC therapy within 60 days after the end of the previous prescription, it will be considered that he discontinued therapy, and the date of the last prescription will be considered as the final date of persistence.

Persistence with OAC therapy will be considered during the period of individual patient follow-up. Patients will be censored at the end of their follow-up period.

- **Major bleeding:** Patients presenting any of the following diagnoses during the follow-up period:

ICD-10	Description
I60	Subarachnoid haemorrhage
I61	Intracerebral haemorrhage
I62	Other nontraumatic intracranial haemorrhage
I690	Sequelae of subarachnoid haemorrhage
I691	Sequelae of intracerebral haemorrhage
I692	Sequelae of other nontraumatic intracranial haemorrhage
S064	Epidural haemorrhage
S065	Traumatic subdural haemorrhage
S066	Traumatic subarachnoid haemorrhage
I850	Oesophageal varices with bleeding
K250	Acute with haemorrhage

Apixaban

B0661148- NON-INTERVENTIONAL STUDY PROTOCOL

Final, 10 October 2019

ICD-10	Description
K252	Acute with both haemorrhage and perforation
K254	Chronic or unspecified with haemorrhage
K256	Chronic or unspecified with both haemorrhage and perforation
K260	Acute with haemorrhage
K262	Acute with both haemorrhage and perforation
K264	Chronic or unspecified with haemorrhage
K266	Chronic or unspecified with both haemorrhage and perforation
K270	Acute with haemorrhage

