K272	Acute with both haemorrhage and perforation
K274	Chronic or unspecified with haemorrhage
K276	Chronic or unspecified with both haemorrhage and perforation
K280	Acute with haemorrhage
K282	Acute with both haemorrhage and perforation
K284	Chronic or unspecified with haemorrhage
K286	Chronic or unspecified with both haemorrhage and perforation
K290	Acute haemorrhagic gastritis
K625	Haemorrhage of anus and rectum
K920	Haematemesis
K921	Melaena
K922	Gastro-intestinal haemorrhage, unspecified
D62	Acute posthaemorrhagic anaemia
H356	Retinal haemorrhage
H431	Vitreous haemorrhage
H450	Vitreous haemorrhage in diseases classified elsewhere
H922	Otorrhagia
I312	Haemopericardium, not elsewhere classified
J942	Haemothorax
R04	Haemorrhage from respiratory passages
K661	Haemoperitoneum
M250	Haemarthrosis
N02	Recurrent and persistent haematuria
N938	Other specified abnormal uterine and vaginal bleeding
N939	Abnormal uterine and vaginal bleeding, unspecified
N950	Postmenopausal bleeding
R31	Unspecified haematuria
R58	Haemorrhage, not elsewhere classified
T792	Traumatic secondary and recurrent haemorrhage

- Ischemic stroke:** Patients who report the following diagnoses in the medical history during the follow-up period:

ICD-10	Description
I63	Cerebral infarction
I64	Stroke, not specified as haemorrhage or infarction

Except I63.6 Cerebral infarction due to thrombosis of cerebral veins, non-pyogenic

- Hemorrhagic stroke:** Patients presenting the following diagnosis in the medical record:

PFIZER CONFIDENTIAL

ICD-10	Description
I60	Subarachnoid haemorrhage
I61	Intracerebral haemorrhage
I62	Other nontraumatic intracranial haemorrhage

- **Systemic embolism:** Patients who report any of the following diagnoses:

ICD-10	Description
I74	Arterial embolism and thrombosis

Definition of covariates

- **Age:** Categorical variable, continues in years. It will be defined from the index date and will be used to assign patients to the following age categories:

18 - 49
 50 - 59
 60 - 69
 70 - 79
 ≥ 80 years old.

- **Charlson Index:** Charlson comorbidity index will be created during the reference period taking into account the following score:

1 point each:

- *Myocardial infarction*

ICD-10	Description
I21	Acute myocardial infarction
I22	Subsequent myocardial infarction
I252	Old myocardial infarction

- *Congestive heart failure*

ICD-10	Description
I110	Hypertensive heart disease with (congestive) heart failure

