I312	Haemopericardium, not elsewhere classified

B: I60, I61, I62, I85.0, I98.3, J94.2, K22.6, K25.0, K25.2, K25.4, K25.6, K26.0, K26.2, K26.4, K26.6, K27.0, K27.2, K27.4, K27.6, K28.0, K28.2, K28.4, K28.6, K29.0, K62.5, K66.1, K76.2, K92.0, K92.1, K92.2

Score 1 point

ICD-10	Description
I60	Subarachnoid haemorrhage
I61	Intracerebral haemorrhage
I62	Other nontraumatic intracranial haemorrhage
I850	Oesophageal varices with bleeding
I983	Oesophageal varices with bleeding, , not elsewhere classified
J942	Haemothorax
K226	Gastro-oesophageal laceration-haemorrhage syndrome
K250	Acute with haemorrhage
K252	Acute with both haemorrhage and perforation
K254	Chronic or unspecified with haemorrhage
K256	Chronic or unspecified with both haemorrhage and perforation
K260	Acute with haemorrhage
K262	Acute with both haemorrhage and perforation
K264	Chronic or unspecified with haemorrhage
K266	Chronic or unspecified with both haemorrhage and perforation
K270	Acute with haemorrhage
K272	Acute with both haemorrhage and perforation
K274	Chronic or unspecified with haemorrhage
K276	Chronic or unspecified with both haemorrhage and perforation
K280	Acute with haemorrhage
K282	Acute with both haemorrhage and perforation
K284	Chronic or unspecified with haemorrhage
K286	Chronic or unspecified with both haemorrhage and perforation
K290	Acute haemorrhagic gastritis
K625	Haemorrhage of anus and rectum
K661	Haemoperitoneum
K762	Central haemorrhagic necrosis of liver
K920	Haematemesis
K921	Melaena
K922	Gastro-intestinal haemorrhage, unspecified

L: INR

Score 1 point

E: Elderly \geq 65 years

Score 1 point

D: E24.4, F10, G31.2, G62.1, G72.1, I42.6, K29.2, K85.2, K86.0, T51, Y90.4, Y90.5, Y90.6, Y90.7, Y90.8, Y91.2, Y91.3, Z50.2, Z71.4, Z72.1

1 or 2 point each

ICD-10	Description
E244	Alcohol-induced pseudo-Cushing's syndrome
F10	Mental and behavioural disorders due to use of alcohol
G312	Degeneration of nervous system due to alcohol
G621	Alcoholic polyneuropathy
G721	Alcoholic myopathy
I426	Alcoholic cardiomyopathy
K292	Alcoholic gastritis
K852	Alcohol-induced acute pancreatitis
K860	Alcohol-induced chronic pancreatitis
T51	Toxic effect of alcohol
Y904	Blood alcohol level of 80-99 mg/100 ml
Y905	Blood alcohol level of 100-119 mg/100 ml
Y906	Blood alcohol level of 120-199 mg/100 ml
Y907	Blood alcohol level of 200-239 mg/100 ml
Y908	Blood alcohol level of 240 mg/100 ml or more
Y912	Severe alcohol intoxication
Y913	Very severe alcohol intoxication
Z502	Alcohol rehabilitation

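### The major-bleeding code list and the Table 2 bleeding row omit four site-specific haemorrhage codes that the protocol lists in HAS-BLED, so a bleed recorded only under one of them can be missed

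*Combined protocol and SAP*

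**What the plan says.** Section 7.3.1 introduces the major-bleeding outcome with "Patients presenting any of the following diagnoses during the follow-up period" and then prints a list of codes. It gives no other criterion and no rule for a bleed outside the list. The bleeding row of Table 2 (baseline variables) uses nearly the same list.

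The HAS-BLED definition in the same section prints two further lists that contain haemorrhage codes:

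- The S item, which the list of abbreviations defines as Stroke: "S: I64, I69.3, D62, D68.3, D69.8, D69.9, H31.3, H35.6, H43.1, H45.0, H92.2, I23.0, I31.2".
- The B item, defined as Bleeding, which begins "B: I60, I61, I62, I85.0, I98.3, J94.2, K22.6, K25.0" and goes on to ulcer and other gastrointestinal bleeding codes. K22.6 is labelled "Gastro-oesophageal laceration-haemorrhage syndrome".

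The stated purpose of the score is given as "The HAS-BLED score will be used to analyze the risk of bleeding". D68.3 appears in the S list with the label "Haemorrhagic disorder due to circulating anticoagulants".

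Outcome information comes from the medical record (Section 7.4.2). Table 1 has Yes/No fields for gastrointestinal, intracranial and other major bleeding. Follow-up stops at a major bleed (Section 7.1). Patients without stroke, systemic embolism or major bleeding form a separate analysis group (Section 7.7).

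**The concern.** A reader who sets the lists side by side finds haemorrhage codes that the protocol recognises at baseline but not as outcomes, with no reason given. The pattern looks like an oversight. Most of the B codes are carried over, and the omitted codes have near neighbours that count.

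Three things are at stake for a patient whose bleed is recorded only under an omitted code:

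- The bleed is not an outcome under the printed definition.
- It does not end follow-up, and the patient falls into the Section 7.7 group treated as free of stroke, embolism and major bleeding.
- At baseline, the same history under I98.3 or K22.6 scores a HAS-BLED bleeding point, while the Table 2 bleeding variable is negative. The two baseline variables then disagree about one patient.

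**Working it through.** The plan states no bleeding rate, expected event count or code count, so there is no figure of its own to reproduce. The check compares the printed lists.

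**Inputs, all from Section 7.3.1 and Table 2**

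- Outcome list (major bleeding): 48 distinct codes.
- Table 2 bleeding row: 45 codes. These are the outcome list without I69.0, I69.1 and I69.2 (48 − 3 = 45).
- HAS-BLED B: 30 codes.
- HAS-BLED S: 13 codes.

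**Differences**

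- B minus outcome: I98.3, K22.6, K76.2. So 30 − 3 = 27 of the B codes are outcomes.
- S minus outcome: D68.3, D69.8, D69.9, H31.3, I23.0, I64, I69.3. So 13 − 7 = 6 of the S codes are outcomes (D62, H35.6, H43.1, H45.0, H92.2, I31.2).
- I64 and I69.3 are stroke codes. Without them, 7 − 2 = 5 haemorrhage-type S codes are missing. With the three from B, 5 + 3 = 8 codes are missing from the outcome list.
- Table 2 is a subset of the outcome list, so it lacks the same eight.
- Outcome minus (S or B): 15 codes, namely I69.0 to I69.2, S06.4 to S06.6, R04, M25.0, N02, N93.8, N93.9, N95.0, R31, R58 and T79.2.

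**Sorting the eight by their printed labels**

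| Code | HAS-BLED item | What the label names | Related code that counts as an outcome |
|---|---|---|---|
| I98.3 | B | bleeding oesophageal varices | I85.0 |
| K22.6 | B | bleeding tear at the gastro-oesophageal junction | K25 to K28 bleeding ulcers, K29.0 |
| H31.3 | S | choroidal bleed | H35.6, H43.1 |
| I23.0 | S | haemopericardium after infarction | I31.2 |
| D68.3 | S | disorder, no site | none |
| D69.8, D69.9 | S | haemorrhagic conditions, no site | none |
| K76.2 | B | liver necrosis; also scored under the liver item | none |

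The first four rows name a bleed at a site, and for each of them the outcome list accepts a bleed of a similar kind. The other four codes do not by themselves establish that a bleed occurred at a site.

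**Size**

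Let f be the share of major bleeds recorded under none of the 48 codes and not otherwise captured. Taken alone, the omission lowers the count of first bleeds by at most f. It is at most f because a patient left in follow-up may have a later, listed bleed. With f assumed to be 1%, 5% or 10%, the relative shortfall is at most 1%, 5% or 10%. This only returns the assumption: the documents give no code frequencies and no value for f.

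**The case against.** There is a fair case for leaving the lists as they are.

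- **The lists serve different purposes.** HAS-BLED is a baseline risk score, and the related Table 1 field covers predisposition as well as history. A risk list may hold conditions that are not events. This stands for D68.3, D69.8, D69.9 and K76.2. It does not explain why one code for bleeding varices is an outcome and another is not.
- **Other routes may capture the event.** The outcome list contains broad codes: K92.0, K92.1, K92.2, D62 and R58, labelled "Haemorrhage, not elsewhere classified". Physicians read the charts, and Table 1 has a field for other major bleeding. This stands in part. A variceal or laceration bleed may well also carry a listed code, which limits the gap. But the protocol does not say that a bleed entered in those fields counts without a listed code. Equally, bleeding history in Table 1 comes from the chart, so the baseline contradiction is certain only under the Table 2 definition.
- **The outcome list is broad elsewhere.** Fifteen of its codes are in neither S nor B, including sequelae codes and unspecified haematuria. This stands, and it bears on direction.

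Stronger readings are tempting. One is that the protocol treats D68.3 as bleeding and then drops it from the safety outcome. In fact D68.3 is printed under S, which means Stroke. The haemorrhage block there looks misplaced, which is a separate matter. Another is that major-bleeding incidence is biased low. Omitted codes alone cannot show that when the list is also wide in other places. A third is that capture differs between warfarin and the NOACs. Nothing in the documents supports different use of these codes by drug, and Section 7.7 rules out treatment comparison.

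**Conclusion.** The inconsistency is real and can be verified from the printed lists. It is clearest for I98.3 and K22.6, which the protocol itself places under Bleeding. It extends to H31.3 and I23.0, which are site-specific haemorrhage codes whose close neighbours count.

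The conclusion is that a bleed recorded only under one of these four codes can be missed, not that bleeds are shown to be missed. It rests on the abstractor applying the printed list strictly and on no listed code being recorded as well. The size cannot be estimated from the documents and is probably small. The net direction of error in incidence is not established. The outcome belongs to an exploratory, descriptive objective. This is a low-severity point, worth acting on because the repair costs almost nothing.

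**What to change.** Before abstraction starts:

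1. Add I98.3, K22.6, H31.3 and I23.0 to the major-bleeding table in Section 7.3.1 (48 + 4 = 52 codes) and to the bleeding row of Table 2 (45 + 4 = 49 codes).
2. Count D68.3 only when the chart documents an actual bleed. Apply the same condition to D69.8 and D69.9 if they are kept.
3. Leave out K76.2 as a liver-necrosis code, and say so. This means that full agreement with the B list is deliberately not sought.
4. State that a chart-confirmed bleed entered in the Table 1 gastrointestinal, intracranial or other-major-bleeding field is classified by the same list.

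The cost is four code rows in each of two tables, a sentence or two of rules, and a short chart check for D68.3. The charts are read in any case.
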